8.2 Enrollment Process

The enrollment process occurs in the following order: Pre-screen, Consent, Enroll, Screen, Randomize or Exclude, Train, Treat, Follow-up.

Pre-screening is optional. Pre-screening may be an informal process to verify age, SARS-CoV-2 test results performed independently by the subject, COVID-19 symptoms, and the onset of symptoms within the past 72 hours. If a subject appears eligible and interested, the subject is consented and considered as officially enrolled. The subject is assigned a subject identification number.

Pre-screening may also be a formal process whereby COVID-19 testing is performed at the clinic to aid in confirming eligibility. In this instance, a pre-screen or testing informed consent is required. (Clinical sites are responsible for developing pre-screen informed consent forms and submission to the IRB for approval.) If a subject appears eligible based on pre-screen results, the subject is consented again and considered as officially enrolled. The subject is assigned a subject identification number.

Following consent, formal screening occurs. The data collected during screening sets baseline values. Screening occurs on Day 1, therefore Screening/Baseline = Day 1. During screening, subjects complete a self assessment of COVID-19 symptoms guided by the site utilizing a grading reference that mimicks what the subjects see in their e-diaires. The data from this self assessment is recorded by the clinical site on source documents. The result of this assessment is auto-calculated in EDC as the composite baseline symptom severity score which is used along with age (40-49 or \geq 50) as stratifying factors for randomization. Following completion of all screening evaluations, the site will use this data to determine eligibility using the inclusion/exclusion criteria. If the subject meets the inclusion/exclusion criteria, they are eligible for randomization. If the subject fails the screening process, they are considered a screen failure. A study exit form is completed for all subjects who received a subject ID number.

Subject data is entered into the RMP (Research Management Platform) EDC system in order to receive randomization to either the active or sham investigational device. Once randomized, the

	Page 40 of 70
EmitBio Inc.	Version: 3.1
EB-P30-01	7 February 2024

subject receives a nasopharyngeal swab for a qPCR test and viral sequencing. Additional information about the subject's COVID-19 exposure and history are recorded. As applicable, a pregnancy test is performed.

Following randomization, the subject is dispensed the assigned device and trained on the use of the device.

8.3 Day 1 Device Assignment, Training, and Treatment

On Day 1, subjects will be assigned either the active or sham device. Training will be provided to the subject on the use of the device.

Other materials will be dispensed to subjects as well including the following:

-SpO2 Monitor

-Thermometer

-SARS-CoV-2 Rapid Antigen Tests

-500mg Acetaminophen to be used as needed for fever based on PI discretion(must be documented as a concomitant medication if used)

- Mobile phone, if necessary the subject is assigned a mobile device to record their self assessments.

The subject is assisted with downloading the eCOA application called Study Hub (electronic mobile app designed as an e-Diary) and trained on how to enter data. A training entry is completed.

Subjects are trained on how to perform daily at home assessments.

Of note, on Day 1, subjects must receive the first in clinic treatment by 1700 hours so that the second at home treatment occurs after 2300 hours but in time to complete the e-diary and televisit before 2400 hours. The e-diary will not allow entries for Day 1 past 2400 hours. The time for the Day 1 PM televisit, as well as for the Day 5 clinic visit, will be scheduled by clinic staff during the Day 1 clinic visit.

Subjects will be advised of the importance of a minimum of 6 hours between the twice daily treatments and should understand that their treatments will be observed either during their clinic or televisits depending on the study day.

At least 30 minutes after the first in clinic treatment, a physical examination of the oropharynx and surrounding tissue will be performed and subjects will be asked to report any local site reactions post the RD-X19 treatment. All solicited local site reactions are considered to be device-related TEAEs and an adverse event form should be completed. Any other unanticipated adverse events are also recorded as applicable.

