7.5 Device Discontinuation

7.5.1 Study Pausing Criteria

If observations of any potential device-related SAE or patterns of non-resolving device-related TEAEs with severity grade 2 or higher in the same System Organ Classification Preferred Term (SOC PT) are observed in a single subject, treatment will be discontinued for that subject and they will continue with the full study schedule including collection of all data as if they had continued to be treated.

EB-P30-01 enrollment may be paused if any of the following events occur:

- Any subject experiences a device-related SAE.
- Any subject experiences laryngospasm, bronchospasm, or anaphylaxis within 2 hours after treatment.
- Two (2) or more subjects experience an allergic reaction such as generalized urticaria (defined as occurring at three or more body parts) within 72 hours after treatment.
 - Potential photo-allergy or phototoxicity to one or more photosensitizing drugs in the subject's medical history should be investigated in all cases. See "Medications that Increase Sensitivity to Light: A 1990 Listing (Levine 1990)."
- Three (3) or more subjects experience a Grade 2 or higher TEAE within the same SOC PT based on the Medical Dictionary for Regulatory Activities (MedDRA) coding, considered to be related to RD-X19.

While the study is paused, a complete review of safety findings will be performed by an Independent Medical Monitor at the earliest opportunity and will make a recommendation to the Sponsor regarding continuation or termination of all or some of the study subjects and/or the overall study protocol. The Independent Medical Monitor has no affiliation with the design or conduct of the trial. The recommendation will be taken under advisement by the study Sponsor who has responsibility for any final decision.

A study volunteer may elect to discontinue participation in the trial at any time. Investigative staff will ask the volunteer to return for an early termination evaluation, but they are under no obligation to do so. All study subjects must return the RD-X19 device at study termination and

	Page 34 of 70
EmitBio Inc.	Version: 3.1
EB-P30-01	7 February 2024

study staff must verify that the device serial number matches the study subject to whom it was assigned.

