 - Subjects will be observed in the clinic for at least 30 minutes post the first RD-X19 illumination. The oropharynx and surrounding tissues will be examined. Reactogenicity assessments will be performed on

Day 1 in the clinic and on days 5, 8, and 14 during clinic evaluations. Interim or unscheduled targeted physical examinations will be performed, if necessary, to evaluate potential TEAEs.

• Vital signs:

Vital sign measurements will include systolic and diastolic BP, HR, breaths per minute, oral temperature and oxygen saturation via a pulse co-oximeter. BP, pulse and respirations and oxygen saturation will be assessed as previously described. Subjects must not eat or drink anything hot or cold within 10 minutes prior to taking their oral temperature or using the RD-X19 device. All subjects will be issued thermometers and small pulse oximeters to measure oral temperature and O₂ saturation on a twice daily basis and record the results on their diary card.

- Urine pregnancy test will be performed locally by the site laboratory at the screening visit. Results will be recorded as study data and referrals made for serological confirmation and follow-up as required.
- e-Diaries: Subjects will be instructed to fill out e-Diaries twice daily to assess their COVID-19 signs and symptoms and record the number of treatments completed. Each of the eight symptoms will be rated on a 4-point scale from none (0) to severe (3). Temperature and oxygen saturation will also be measured and recorded via devices provided by site personnel and taken home by the subject. Televisit contact will be made by with subjects by the decentralized study staff during the home treatments on days 1-7. Observation of use of the device and recording of study data should be timed to coincide with the study subject encounter. Daily contact with study subjects will enhance safety monitoring and reinforce adherence to at-home study procedures.
- COVID-19 Severity Progression
 - There is a risk that subjects with mild COVID-19 may progress to moderate or more severe disease while on study. In such cases, appropriate medical referrals for evaluation and treatment outside of the protocol will be made.
 - Medically attended visits as a result of COVID-19 will be classified into the following categories:
 - 1) those who require medical attention attributed to any severity of COVID-19;

- 2) those who require medical attention attributed to any SAE;

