8.6.1 Definition of Treatment Emergent Adverse Event (TEAE)

Adverse Events (AEs) are any untoward medical occurrence, unintended disease or injury, or untoward clinical signs (including abnormal laboratory findings) in subjects, whether or not related to the investigational medical device and whether anticipated or unanticipated. TEAEs are adverse events (AEs) that either start after initial treatment, or which are present prior to treatment initiation but which increase in severity after treatment. No AEs that are not TEAEs are expected in this study since the time between enrollment and first treatment is very brief.

Any medical condition that is present at the time that the subject is screened will be captured as part of the study subject's baseline medical history and will serve as the basis for capturing AEs that are treatment-emergent based on worsening severity.

TEAEs can be further divided into solicited TEAEs and unsolicited TEAEs. Solicited TEAEs are those for which the study team will specifically query the subject whether they occurred. Unsolicited TEAEs are those events that the subject report occurring without being queried about the specific event.

All TEAEs will be assessed for severity and relationship to study intervention/investigational device. Reporting of all TEAEs, solicited and unsolicited, will occur during the period from study device administration on Day 1 through Day 14 or until an early termination visit.

All TEAEs, solicited and unsolicited, will be captured on the appropriate source documents and e-CRFs. Information to be collected for TEAEs includes event description, date of onset, assessment of severity, relationship to study product and alternate etiology (assessed only by those with the training and authority to make a diagnosis such as the participating clinical site PI or appropriate sub-investigator), date of resolution, seriousness, and outcome. All TEAEs will be documented regardless of relationship.

TEAEs will be followed to resolution or stabilization.

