### 8.5.3. Adverse Events

All adverse event (AE) tables will be produced for the Safety population, and will be presented by treatment group. The AE incidence tables will all be based on treatmentemergent adverse events (TEAEs), but all listing-type tables and the AE data listing will also include non-treatment-emergent AEs. A TEAE is defined to be an AE which starts after initiation of treatment, or a medical condition which was present prior to initiating treatment but which increases in severity after starting treatment. TEAEs will be captured and identified by the investigator who will assess the increase in severity part of the TEAE definition by comparing post-baseline Medical History/Physical Examination with baseline Medical History/Physical Examination. The only possible non-TEAEs recorded could be those AEs experienced between signing the ICF and the time of the first treatment, but as this time period is very short it is expected that there will be very few if any AEs that are not TEAEs. All AEs will be coded using MedDRA version 23.0 or higher.

The following 12 incidence tables will be produced for TEAEs which for #2-#8 will be sorted by system organ class (SOC) and preferred term (PT):

- 1. Overall TEAE summary table (with counts for #2-#12)
- 2. TEAE incidence table
- 3. Treatment-emergent SAE (TESAE) incidence table (including a separate count for any deaths)
- 4. TEAE incidence table by severity
- 5. Device-Related TEAE (DR-TEAE) incidence table
- 6. DR-TEAE incidence table by severity
- 7. Anticipated DR-TEAE incidence table
- 8. Unanticipated DR-TEAE incidence table overall and by severity
- 9. Solicited TEAEs incidence table overall and by severity
- 10. Solicited DR-TEAEs incidence table overall and by severity
- 11. TEAEs leading to discontinuation of treatment incidence table

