#### 12. TEAEs leading to discontinuation from the study - incidence table

For subjects experiencing the TEAE more than once only the most severe will be counted in the incidence tables.

Anticipated DR-TEAEs are those described in Protocol Section 5.2.1, and are anticipated provided that all of the following applies: (i) occurred post-treatment with severity of mild; (ii) did not lead to discontinuation of treatment; and (iii) did not lead to discontinuation from the study. Anticipated DR-TEAEs will be identified by a pre-specified list of MedDRA coded terms or a listing will be provided to Quantics with an identifying flag for any AEs that correspond to an anticipated DR-TEAE.

Unanticipated DR-TEAEs include those TEAEs reported as device-related and which are not described in Protocol Section 5.2.1. In addition, those TEAEs described in Protocol Section 5.2.1 for which any of the following occurs will also be classified as unanticipated: (i) occurred post-treatment with severity of moderate or severe; (ii) led to discontinuation of treatment; or (iii) led to discontinuation from the study.

Solicited TEAEs are those collected by direct questioning of study subjects and are recorded on the CRF pages for Reactogenicity assessment including oropharyngeal assessment. [Unsolicited TEAEs are those spontaneously reported by the subject and/or in response to an open question from study staff or revealed by observation, physical examination, or other diagnostic procedure.] The incidence tables for solicited TEAEs, as derived from the Reactogenicity CRF page, will summarize:

- Clinical judgement (normal, abnormal not due to device, abnormal due to device)
- Pain (absent, present [overall and separate counts for mild, moderate, severe])
- Erythema at the illumination site (absent, present [overall and separate counts for mild, moderate, severe])
- Edema/induration at the illumination site (absent, present [overall and separate counts for mild, moderate, severe])
- Any other pain, redness, swelling or lesion of the oral mucosa (absent, present [overall and separate counts for mild, moderate, severe])

Subjects experiencing the individual solicited TEAE more than once will be counted in the incidence tables under the most severe category. For "Clinical judgement" here also only the most severe will be counted (where "abnormal due to device" is regarded as the "most severe" for this purpose).

The following listing-type tables will be produced:

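### The solicited oral-reaction items have no specified pre-treatment grade and the SAP tables no new-or-worse rule, so existing COVID-19 throat findings can be counted as treatment-emergent

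*Protocol*

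**What the plan says.** **Definition.** Under Protocol 8.6.1 a TEAE is an event that starts after the first treatment, "or which are present prior to treatment initiation but which increase in severity after treatment". The same section divides TEAEs into solicited and unsolicited. Protocol 8.6.2 lists the solicited ones: pain, erythema and edema/induration at the illumination site, and any other oral mucosal finding.

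**Timing.** Protocol 8.3 states: "At least 30 minutes after the first in clinic treatment, a physical examination of the oropharynx and surrounding tissue will be performed". Protocol 8.6 repeats the order: "Subjects will be observed in the clinic for at least 30 minutes post the first RD-X19 illumination", followed by the oropharynx examination. Reactogenicity is assessed on "Day 1 in the clinic and on days 5, 8, and 14 during clinic evaluations". The Schedule of Activities (Protocol 4.7) marks an oropharyngeal assessment in the baseline column, and SAP 3.4 lists oropharyngeal exams at the baseline visit. Neither says whether these come before or after the first treatment.

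**Attribution.** Protocol 8.3: "All solicited local site reactions are considered to be device-related TEAEs and an adverse event form should be completed".

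**Tabulation.** SAP 8.5.3 derives the solicited tables (9 and 10) from the Reactogenicity CRF page, with rows such as "Pain (absent, present [overall and separate counts for mild, moderate, severe", and counts each subject once at the worst grade. The SAP's general TEAE text has the investigator judge worsening by "comparing post-baseline Medical History/Physical Examination with baseline Medical History/Physical Examination".

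**The concern.** To decide whether a finding is new or worse, one needs its state before treatment on a comparable scale. The solicited items are what acute pharyngitis produces, and sore throat counts towards inclusion criterion 3. If the first graded look at these items comes after the device has been used, and the table counts whatever is present, disease already there can enter as a device-era event.

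Safety is half of the study's stated primary goal, and mild local reactions are the main expected harm in Protocol 5.2.1. Existing findings counted in both arms raise both rates and make a real RD-X19 excess harder to see. There is a secondary route into oversight. The pausing criterion in Protocol 7.5.1, "Three (3) or more subjects experience a Grade 2 or higher TEAE within the same SOC PT", is limited to events considered related to RD-X19, and Protocol 8.3 makes solicited local reactions device-related by rule.

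**Working it through.** The documents give no figure to reproduce here. The check sets the texts side by side and then illustrates the dilution.

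**1. Is a pre-treatment grade on the four items required anywhere?**
- Protocol 8.2 puts screening before randomization and treatment, but also equates screening/baseline with Day 1. The baseline column in 4.7 contains Treatments and TEAE Assessments as well. Its oropharyngeal mark could therefore be the post-treatment exam.
- Before treatment there are a full physical examination including the throat (Protocol 8.1.3), an exclusion for oral abnormalities (criterion 15) and a 0-3 self-score for sore throat (Protocol 8.1.2). SAP 8.5.5 records throat only as normal, or abnormal with or without clinical significance.
- SAP 7.6 tabulates the baseline sore-throat score but no oropharyngeal findings. The reactogenicity listing in SAP 8.5.3 covers Days 1, 5, 8 and 14/early termination, with no separate pre-treatment record.

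No text requires the four items to be graded before treatment.

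**2. Do tables 9 and 10 apply the new-or-worse rule?** Their description gives presence, severity and worst category, with no reference to a prior state. The protocol's first item is pain at the illumination site. The SAP row is plain pain, although the SAP keeps the site qualifier for erythema and edema. Ordinary COVID-19 throat pain fits that row.

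**3. Do other texts remove existing findings?** Protocol 9.4.2 excludes COVID-19 signs and symptoms from TEAEs; the SAP definition does not repeat this. The SAP's clinical-judgement row has a category for abnormality not due to the device, but it is a separate row that does not filter the pain or erythema rows. It also sits badly with the Protocol 8.3 attribution rule.

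**4. Illustration of dilution (assumed rates).** Per arm n = 326/2 = 163. Let q be the share with an existing finding that is counted, and r the true new-reaction rate among the remaining RD-X19 subjects, with none in sham. Then:
- RD-X19 shown: a = q + (1 − q)r
- Sham shown: s = q
- Difference: (1 − q)r
- SE = √{[a(1 − a) + s(1 − s)]/163}

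With r = 5%:

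| q | RD-X19 | Sham | Difference | SE (points) | Power |
|---|---|---|---|---|---|
| 0 | 5.0% | 0% | 5.0 | 1.7 | 0.83 |
| 20% | 24.0% | 20.0% | 4.0 | 4.6 | 0.14 |
| 40% | 43.0% | 40.0% | 3.0 | 5.5 | 0.08 |
| 60% | 62.0% | 60.0% | 2.0 | 5.4 | 0.06 |

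Power is for a two-sided 5% comparison: Φ{[(a − s) − 1.96·SE₀]/SE}, with SE₀ = √[2p̄(1 − p̄)/163] and p̄ = (a + s)/2. For q = 40%: p̄ = 0.415, SE₀ = 0.0546, (0.030 − 1.96 × 0.0546)/0.0546 = −1.41, Φ = 0.08. Between q = 0 and q = 40%, power falls from 0.44 to 0.04 for r = 2%, and from 0.99 to 0.19 for r = 10%. No test of these tables is planned, so power serves only to express the dilution.

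**The case against.** The strongest reply is that a baseline exists and the rule is already written. An oropharyngeal assessment is marked at baseline, the throat is examined at screening, oral abnormality is exclusionary, and sore throat is self-graded on wording close to the TEAE severity scale. Protocol 8.6.1 says conditions present at screening are the basis for judging worsening, and it covers solicited events. Protocol 9.4.2 excludes COVID-19 symptoms. The SAP tabulates severity and a not-due-to-device judgement. Existing findings should balance across randomized arms, and nothing formal depends on these tables.

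Much of this stands, and it rules out three stronger readings that a reader might infer:
- **That the throat is not assessed or graded at all before treatment.** It is examined, and sore throat is scored. What is missing is a required pre-treatment grade on the reactogenicity items.
- **That existing findings will certainly be counted.** Investigators may apply the general definition when completing the page. The CRF was not available and may hold more than the text says.
- **That a large share of each arm will be affected, or that the pausing threshold will be met early.** No baseline rate is given, the criterion requires relatedness, and it says only that enrollment may be paused. Protocol 4.1 reports no local site reactions in the earlier 31-subject trial and no predefined pausing or stopping signal in the 216-subject trial. Those CRFs are not shown, so this is not proof, but it does not point to a large effect.

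What the reply does not do is connect the baseline information to tables 9 and 10. Balance between arms prevents bias in the simple difference from existing findings alone, but it does not prevent the dilution shown above.

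**Conclusion.** The concern holds as a gap between definition and measurement. The only Day 1 oropharynx examination with a stated time follows treatment, no text requires the four solicited items to be graded beforehand, and the solicited tables do not apply the new-or-worse rule. Followed as written, the plan can count COVID-19 throat pain or redness as solicited TEAEs in both arms and, under Protocol 8.3, as device-related.

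The direction is clear: higher rates in both arms and a weaker contrast. The size is not known. The illustration assumes every existing finding is recorded and true reactions arise only in subjects without one; the severity rows would recover some information where a finding worsens. The tables are descriptive and no efficacy result is affected. This is a worthwhile, inexpensive improvement to the safety data rather than a threat to the trial's main conclusion.

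**What to change.** - **Protocol 8.3 and 4.7:** complete the same four graded items at the screening throat examination, and state that this precedes the first treatment. Keep the examination at least 30 minutes afterwards as the first post-treatment assessment.
- **SAP 8.5.3, tables 9 and 10:** count an item only if it was absent before treatment or is of higher grade afterwards. Show pre-treatment prevalence by item and arm alongside. Use the same site qualifier for pain as Protocol 8.6.2.
- **Reconcile** the Protocol 8.3 attribution sentence with the COVID-19 exclusion in Protocol 9.4.2, the TEAE definition in SAP 8.5.3 and the SAP's not-due-to-device category. Which attribution rule applies is for the sponsor to settle; the texts need to agree, because the answer also determines what reaches the Protocol 7.5.1 count.

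The cost is about a minute of site time, one extra instance of an existing CRF page and a few lines of text. The drawback is that solicited counts become change-from-baseline counts and are less directly comparable with earlier RD-X19 studies. Also tabulating the unadjusted post-treatment presence would soften that.
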